12.2 Study Design and Objectives

This is a randomized placebo controlled Phase II study of GVAX versus placebo vaccination given early after allogeneic HSCT in high risk AML/MDS patients. The premise is that GVAX vaccination early after HSCT will increase progression-free survival (PFS) in this patient population. The target accrual goal is 106 eligible patients for vaccination, 53 per each arm, over a 3.8 year period and followed for an additional 18 months. This design will give approximately 80% power to detect a 75% increase in 18 month PFS in the GVAX arm (Arm A) compared to the placebo arm (Arm B) as graphically illustrated in Figure 1.

12.3 Accrual

Based on the accrual of the DFCI transplant group between 2006 and 2011, the projected accrual rate will be approximately 40 high risk AML/MDS patients with active disease who meet the eligibility criteria per year. Of these 40 eligible patients, we anticipate that about 30% will not meet the criteria for starting GVAX/Placebo administration outlined in Section 5.3.1. Based on this projection, it is anticipated that approximately 3.8 years of accrual will be necessary to enroll the targeted sample size of 106 eligible patients for vaccination. Accounting for the 30% attrition, we anticipate that about 152 patients will be enrolled on the study to obtain 106 patients eligible to start vaccination.

12.4 Randomization

After enrollment, patients will be randomized at a ratio of 1:1 between two arms using permuted block algorithm within strata. Randomization will be stratified by center (DFCI, BIDMC, MGH), disease (AML vs. MDS), age (≥50 vs. <50), and conditioning intensity (myeloablative Fly/Bu4 vs. RIC Flu/Bu2).

12.5 Sample Size and Power Calculations

In our previous study¹⁰, the 2-year progression-free survival for 15 patients who received at least one vaccination was 46%. This estimate compared to 18% 2-year PFS from our contemporaneous control cohort that was most similar to those patients in the GVAX trial. Extrapolating this information, we hypothesize that the PFS will be increased by 75% at 18 months post randomization in Arm A (GVAX) compared to Arm B (placebo). A retrospective analysis of high risk AML/MDS patients who underwent myeloablative or RIC HSCT between 2004 and 2008 at DFCI shows that a small portion of patients are cured from the underlying disease after allogeneic HSCT and the distribution of PFS follows a two-component exponential cure rate model (Figure 1). Basing the fitted curve in Figure 1 as the null hypothesis, we hypothesize that the PFS will be increased by 75% from 26% to 46% by 18 months post HCT in Arm A. More specifically, the proposed alternative hypothesis is H_A: S_A > S_B,

where S_A and S_B denote the distributions of PFS in Arms A and B, as shown in (1) and (2), respectively

$$\begin{split} S_A &= 0.45 + 0.45 * exp(-t*(log(2)/2.5)) + 0.1*exp(-t*(log(2)/4.5)) \ (1) \\ S_B &= 0.24 + 0.76 * exp(-t*(log(2)/3.5)) \end{split} \tag{2}$$

This projection incorporates approximately 30-45 days of wait time from randomization to the start of GVAX/Placebo vaccination and additional ~40 days for the administration of a serial of 6 vaccinations. During this period, we expect little difference in PFS between two arms. Figure 4 depicts (1) and (2) graphically. With this design, 106 eligible patients with 69 events will be required to achieve approximately 80% power with one-sided significance level of 0.15. Since this is a direct but nondefinitive randomized comparison to a standard treatment control, we follow recommendations made by Rubinstein et al. ^{18, 19} and use a one-sided type I error rate of 0.15 with 80% power ¹⁸⁻²⁰. The power calculation is calculated using the R program, *Powlgrnk* (developed by [name] at DFCI), which computes power of the two-group log-rank test for arbitrary failure time distributions and has been used for non-proportional hazards alternative.²¹

[figure not shown]

Figure 4. Target PFS. Blue line represents the projected PFS distribution in Arm A (GVAX) and red line represents the projected PFS distribution in Arm B (Placebo). The solid black line is the Kaplan-Meier curve from the historical control

12.6 Interim Analyses

The study will be monitored using standard procedures and processes by an independent Data and Safety Monitoring Committee (DSMC) of the Dana-Farber Harvard Cancer Center (DF/HCC). Interim analysis for efficacy will occur annually starting at 33% information time, which is anticipated to occur approximately 2.8 years after the start of the trial. The interim results will be reported to the DF/HCC DSMB annually. However, these interim inspections will not have an effect in terms of

stopping accrual to the study and terminate the study early in favor of alternative (superiority) or null hypothesis (futility). This is because i) due to a small sample size at each interim look, stopping early for futility would result in substantially wide confidence intervals, larger Type II error, and thus leading to greater uncertainty about the magnitude of the PFS difference, ii) even if the PFS difference is not as large as targeted, investigators are interested in learning the magnitude of the PFS difference for further investigation, iii) stopping early for superiority would provide less safety data than planned and potential difficulty with the efficacy analysis and its interpretation.

12.7 Guidelines for Grade III-IV acute GVHD and serious toxicity

Monitoring of key safety endpoints (grade 3 or higher treatment related toxicity, grade III-IV acute GVHD) will be conducted in accordance with the DF/HCC DSMB meeting. GVAX was well tolerated in the previous trial (DFCI#04023). For the entire cohort of 24 patients that included 9 patients without vaccination, the incidence rate of grade III-IV acute GVHD was 4%, which is comparable to 9% in a historical control cohort of patients whose patients and transplant characteristics were most similar to those in the GVAX trial. Based on this information, we do not anticipate that GVAX will be associated with an increased risk of grade III-IV aGVHD nor severe toxicity. However, we will compare the grade III-IV aGVHD rate and grade 3 or higher treatment related toxicity rate between two arms at each interim look. If, at any interim look, this difference is significant at the two-sided level of 0.05, this would trigger a consultation with the DF/HCC DSMB for additional review.

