11.2 Safety Meetings

The DF/HCC Data and Safety Monitoring Board (DSMB) will review and monitor study progress, toxicity, safety and other data from this trial. The board is chaired by a medical oncologist from outside of DF/HCC and has external and internal representation. Information that raises any questions about participant safety or protocol performance will be addressed with the Principal Investigator, statistician and study team members. Should any major concerns arise, the DSMB will offer recommendations regarding whether or not to suspend the trial.

The DSMB will meet twice a year to review accrual, toxicity, response and reporting information. Information to be provided to the DSMB may include: participant accrual, treatment regimen information, adverse events and serious adverse events reported by category, summary of any deaths on study, audit results, and a summary provided by the study team. Other information (e.g. scans, laboratory values) will be provided upon request.

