12.8 Statistical Analysis Plan

The primary analysis will be the modified ITT analysis for the primary endpoint of PFS at 18 months after randomization. The primary analysis will be performed using the Kaplan-Meier estimates for PFS for each arm at 18 months along with 95% confidence intervals. Several secondary analyses of PFS will be conducted, depending on an assessment of the original assumption of non-proportional hazards assumed in the study design. First of all, graphical and analytical diagnostics will be used to assess the presence of non-proportional hazards between treatment arms. If there is no evidence of nonproportional hazards, a relative risk will be estimated from the Cox model both unadjusted and adjusted for other covariates. To assess the effect of GVAX, several approaches will be taken: 1) inclusion of the treatment arm as a fixed covariate in a model, 2) inclusion of the total number of GVAX vaccinations (0-6) as a fixed covariate in a model, 3) treating the number of GVAX/placebo vaccinations as a time dependent repeated measures and an interaction between the number of vaccinations and the treatment arm in a model, 4) exploring a joint model for survival and longitudinal data. 26 If there appears to be non-proportional hazards, several analyses will be conducted: 1) a comparison of PFS at 18 months post randomization will be conducted using the linear combination test proposed by Logan et al.^{24, 28.29} This method directly compares the PFS curves starting at 18 months, and accounts for patients enrolled early in the study having additional follow-up past 18 months. 2) a pseudo value regression approach³⁰, 3) PFS from the start of vaccination will be analyzed, 4) multivariable cure rate model will be performed as described in Ibrahim et al.²⁷

Secondary objectives include relapse and non-relapse mortality (NRM), acute and chronic GVHD, overall survival. For the comparison of GVHD, NRM and relapse, we will perform competing risks data analysis using Gray test and competing risks regression analysis.²⁵ All laboratory correlative studies will be analyzed using appropriate statistical methods. In particular, the effect of vaccination on infiltration of dendritic cells, macrophages, granulocytes, and lymphocytes as well as T cell reconstitution will be examined by comparing pre to post vaccination data and the GVAX to the

placebo arm.

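### Section 12.7 states its by-arm safety comparison and trigger only for the interim looks, which start at about 2.8 years, and not for the earlier twice-yearly DSMB meetings

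*Combined protocol and SAP*

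**What the plan says.** Section 12.7 opens by linking monitoring of both safety endpoints to the board's calendar: treatment-related toxicity of grade 3 or higher and "grade III-IV acute GVHD) will be conducted in accordance with the DF/HCC DSMB meeting". Section 11.2 sets that calendar: "The DSMB will meet twice a year to review accrual, toxicity, response and reporting information".

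The comparison itself is put on another clock. Section 12.7 goes on: "we will compare the grade III-IV aGVHD rate and grade 3 or higher treatment related toxicity rate between two arms at each interim look". The consequence is that if "this difference is significant at the two-sided level of 0.05, this would trigger a consultation with the DF/HCC DSMB" for additional review.

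Section 12.6 is the only place that schedules looks. They are efficacy analyses, held "annually starting at 33% information time, which is anticipated to occur approximately 2.8 years after the start of the trial", and it adds: "The interim results will be reported to the DF/HCC DSMB annually". Section 12.6 uses the term *interim look* for these analyses, the same term as in 12.7.

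Two other places bear on the point. Section 6.1.1.7 puts the between-arm comparison of severe acute GVHD in the planned interim analyses. Section 12.8 says "For the comparison of GVHD, NRM and relapse, we will perform competing risks data analysis using Gray test", but gives no interim timing.

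**The concern.** Section 6.1.1.7 accepts that the vaccine might cause or worsen GVHD. Safety is also the only interim comparison with a stated consequence, because 12.6 says the efficacy looks will not stop the trial. Read literally, the first between-arm safety comparison waits for a date set by PFS information. By then some 34-38 patients have started GVAX, and the board has met about five times without a stated by-arm table or trigger. The reasons 12.6 gives for its non-stopping looks concern estimation of the PFS difference and the amount of safety data. They do not explain why a safety comparison should wait for those looks.

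**Working it through.** **Inputs from the plan.** 106 patients eligible for vaccination, 53 per arm, 3.8 years of accrual and 18 months of further follow-up (12.2); 30-45 days from randomization to first vaccination and 69 events (12.5); first look at 33% information, about 2.8 years (12.6); historical control grade III-IV acute GVHD rate 9% (12.7).

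**Assumptions not in the plan.** Uniform accrual; a DSMB cycle that starts with the trial; lags up to 120 days; GVAX GVHD rates of 18% and 25%; a 20-30% toxicity rate; independent endpoints; and the test, since 12.7 names none.

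**1. Reproducing 2.8 years.** If information means patients with 18 months of follow-up, 33% is reached at 0.33 × 3.8 + 1.5 = 2.75 years, which matches. If it means events, 33% of 69 is about 23 events. The design curves in 12.5 give that number at 19.7 months, about 1.6 years. The plan does not define the term; its stated date fits the first meaning.

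**2. Started vaccination at 2.8 years.** Share = (2.8 − lag in years) / 3.8.
- 30 days: (2.8 − 0.082)/3.8 = 71.5%, or 75.8 patients, 37.9 on GVAX.
- 45 days: (2.8 − 0.123)/3.8 = 70.4%, or 74.7 patients, 37.3 on GVAX.
- 120 days (assumed): (2.8 − 0.329)/3.8 = 65.0%, or 68.9 patients, 34.5 on GVAX.

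**3. Meetings before the first look.** At 0.5, 1.0, 1.5, 2.0 and 2.5 years: five. On the events reading (1.6 years) there are three, with about 34-41% of patients started.

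**4. What earlier comparison would gain.** Exact sequential enumeration of two binomials with Fisher's test at two-sided 0.05, counting everyone who has started as fully assessed. With a 30-day lag the twice-yearly looks have 6, 13, 20, 27, 34, 41, 48 and 53 per arm, and the annual looks 38, 52 and 53. With a 120-day lag they have 2, 9, 16, 23, 30, 37, 44, 51 and 53, against 34, 48 and 53. Ranges cover lags of 30-120 days.

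| GVHD rate, placebo v GVAX | Twice-yearly: flagged by 2.5 y | As written: flagged at 2.8 y | Overall, twice-yearly v as written |
|---|---|---|---|
| 9% v 25% | 31-36% | 31-36% | 59% v 55% |
| 9% v 18% | 12-14% | 10-13% | 25-26% v 22% |

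For 9% v 25%, the mean number of GVAX patients started when harm is flagged is 32.1-32.6 with twice-yearly looks and 40.9-42.8 as written. The first meeting contributes 1% or less.

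**5. Sensitivity to the test.** A simulation with a Gray-type test that allows for incomplete follow-up shows the same pattern for 9% v 25%: a mean of about 30-31 v 41-43 GVAX patients at a flag, and overall detection of 69-71% v 65-67%.

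**6. False flags over both endpoints.** Combined rate = 1 − (1 − a)(1 − b), where a and b are the rates for the two endpoints. Fisher: 7-8% as written, 11-13% twice-yearly. Unadjusted chi-square: 15-18% and 27-35%. For GVHD alone with the Gray-type test: 8-9% and 13-14%.

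**The case against.** The strongest reply is that safety oversight does not wait for 2.8 years. The DSMB reviews toxicity twice a year and can recommend suspension (11.2). Non-hematologic events of grade 3 or higher, hematologic events of grade 4 or higher and deaths go to the IND sponsor and principal investigator within 2 working days, whatever the attribution (10.3). Adverse events and GVHD are assessed weekly during vaccination (9.0). All of this stands, and a reader who inferred that safety goes unmonitored until the first look would be wrong. These provisions do not, however, state a comparison between arms.

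Nor do the documents show that the board is denied by-arm data. The list in 11.2 is not exhaustive, it adds "Other information (e.g. scans, laboratory values) will be provided upon request", and nothing says the board is blinded. The authors may have meant *interim look* to include every DSMB meeting, as the opening of 12.7 suggests. Section 6.1.1.7 does not settle this: it covers GVHD only and points to a section 13.7 that does not exist. If the wider meaning was intended, the text needs to say so.

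It is also tempting to set the 31-36% flagged by 2.5 years against none as written. That stops the clock just before the planned look, which flags 31-36% itself.

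Finally, nothing in the documents predicts a 25% rate. Section 12.7 reports 4% in the pilot's whole cohort against 9% in controls and expects no increase. That is fair, and 25% is a large-harm scenario. The pilot is small, though. If its report of no grade 3-4 GVHD (2.4.2) is taken as 0 of 15 vaccinated, the one-sided exact 95% upper limit is 1 − 0.05^(1/15) = 18%, so the milder scenario is not excluded.

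**Conclusion.** The point holds as a gap in what 12.7 states. No by-arm comparison or trigger is given for about five DSMB meetings before 2.8 years, or about three if information means events. It does not hold as a claim that oversight is absent or that by-arm data are withheld.

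The benefit is mainly timing: about 9-10 fewer GVAX patients started before a flag if the true rates were 9% and 25%, with overall detection up by about 4 percentage points. At 9% v 18% the gain in detection is of similar size (about 3-4 points) from a much lower base. These figures rest on the assumed GVAX rates, uniform accrual, Fisher's test and full assessment of everyone started. The textual gap needs none of them. The change is optional but cheap, and confidence is medium because 12.7 can be read more generously.

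**What to change.** In 12.7, state that by-arm rates of grade III-IV acute GVHD and grade 3 or higher treatment-related toxicity go to the DSMB in closed session at each twice-yearly meeting, separately from the PFS looks. The existing two-sided 0.05 level would mark a difference for additional DSMB review.

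Name the test: Fisher's exact test for rates, or Gray's test for GVHD to agree with 12.8. An unadjusted chi-square should not be used, because repeated twice-yearly it gives false flags in 27-35% of trials over both endpoints.

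Have the tables prepared by an unblinded statistician firewalled from the study team. Section 4.2 keeps study personnel outside the cell facility blinded, and 11.1.1 has the coordinator working with the registration office on data, so the separation should be written down. In the same edit, define information time in 12.6 and correct the cross-reference in 6.1.1.7.

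The cost is protocol wording, a short table at meetings already scheduled, and more false flags: from about 7-8% to 11-13% over both endpoints with Fisher's test, assuming a 20-30% toxicity rate and independent endpoints. Each leads only to DSMB review.

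### The section 12.7 harm trigger is two-sided at 0.05 with no named test, so it would usually stay silent if GVAX doubled grade III-IV acute GVHD

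*Combined protocol and SAP*

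**What the plan says.** Under section 12.7, "we will compare the grade III-IV aGVHD rate and grade 3 or higher treatment related toxicity rate between two arms at each interim look". The rule that follows is: "If, at any interim look, this difference is significant at the two-sided level of 0.05, this would trigger a consultation with the DF/HCC DSMB". The section names no test, sets no harmful difference to detect and gives no operating characteristics. As background it reports that in the earlier GVAX trial "the incidence rate of grade III-IV acute GVHD was 4%, which is comparable to 9% in a historical control cohort", and it expects no increase from the vaccine.

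Section 6.1.1.7 accepts that the vaccine might provoke or worsen GVHD. It relies on the planned interim comparison of grade 3-4 acute GVHD, citing a section 13.7 that does not exist; 12.7 is evidently meant.

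Section 12.6 places interim looks annually from about 2.8 years and rules out early stopping for efficacy or futility. Sections 12.2 and 12.5 set the size: "With this design, 106 eligible patients with 69 events will be required to achieve approximately 80% power with one-sided significance level of 0.15". Section 11.2 separately has the DSMB review toxicity twice a year.

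**The concern.** A trigger for consultation is a screening device. A false alarm costs one extra discussion. A miss means that the plan's own rule does not prompt a focused look at a GVHD imbalance while patients are still being vaccinated. That argues for a sensitive, one-directional rule.

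Section 12.7 instead uses the conventional two-sided 0.05. This leaves 0.025 in the direction of harm and spends the other half on GVAX having less GVHD, which needs no safety consultation. With small arms and an uncommon event, the rule may rarely fire even when the rate has doubled. Because no test is named, two analysts could also apply different rules to the same data.

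**Working it through.** **Inputs.** There are 106 patients, 53 per arm, accrued over 3.8 years (12.2). Looks are annual from about 2.8 years (12.6). Placebo rates of 9% and 4% are the two figures in 12.7. The doubling is a benchmark chosen for this review; the plan sets none.

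**The plan's own figure.** None is given for the trigger. The efficacy design reproduces: the curves in 12.5 give 18-month PFS of 0.262 and 0.459, 69.3 expected events and a simulated power of 81.5%, against the stated 69 events and about 80%. The sample size used below is therefore consistent with the design.

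**Patients at the looks.** With uniform accrual, 106 × 2.8/3.8 = 78, or 39 per arm at the first look. At 3.8 years there are 53 per arm.

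**What it takes to fire, 39 per arm.** With x cases on GVAX and none on placebo, the one-sided Fisher p is C(39,x)/C(78,x), and the two-sided p is twice that:
- 3 v 0: 9,139/76,076 = 0.120 one-sided.
- 4 v 0: 82,251/1,426,425 = 0.058 one-sided, 0.115 two-sided.
- 5 v 0: 575,757/21,111,090 = 0.0273 one-sided, 0.055 two-sided.
- 6 v 0: 3,262,623/256,851,595 = 0.0127 one-sided, 0.025 two-sided.

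Two-sided Fisher at 0.05 therefore needs 6 v 0. With more placebo cases, the full hypergeometric tail gives 8 v 1, 9 v 2 and 11 v 3. The uncorrected chi-square needs 4 v 0, 6 v 1 and 8 v 2.

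**Chance of firing at the first look, 18% v 9%.** The pooled normal approximation is Φ[(d − 1.96·SE0)/SE1], with:
- d = 0.09
- SE0 = √(2 × 0.135 × 0.865/39) = 0.0774
- SE1 = √((0.18 × 0.82 + 0.09 × 0.91)/39) = 0.0767

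This gives Φ(−0.80) = 0.21. Exact binomial enumeration gives 0.22 (chi-square) and 0.13 (Fisher). At 53 per arm it gives 0.27 and 0.18.

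**Chance of firing at either look** (39 then 53 per arm, cumulative data):

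| Rule | 18% v 9% | 8% v 4% | 9% v 9% |
|---|---|---|---|
| Two-sided 0.05, Fisher | 21% | 5% | about 2.5% |
| Two-sided 0.05, chi-square | 31% | 16% | 8% |
| One-sided 0.10, Fisher | 46% | 20% | 6% |
| One-sided 0.10, score | 59% | 42% | 15% |

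For the two-sided rules, the last column counts firing in either direction; in the harm direction alone it is about 1% (Fisher) and 4% (chi-square).

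**Sensitivity to look times.** With looks at 18, 35 and 53 per arm, the current rule fires in 22% (Fisher) or 34% (chi-square) at 18% v 9%, and in 5% or 16% at 8% v 4%. The conclusion does not depend on the schedule.

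**Larger harm.** For 27% v 9% at the first look, the current rule fires with probability 0.46 (Fisher) or 0.57 (chi-square).

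**Why the score test is not the example used in the fix.** At 2 v 0 with 39 per arm, the pooled rate is 2/78 = 0.0256, the SE is √(0.0256 × 0.9744 × 2/39) = 0.0358, and z = 0.0513/0.0358 = 1.43. That exceeds 1.28, so two cases against none would trigger.

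**The case against.** The strongest reply is that the trigger is an addition to oversight that already exists. Section 11.2 has the DSMB review toxicity twice a year. Section 10.3 sends grade 3 or higher non-hematologic events, whatever their attribution, to the IND sponsor and the principal investigator within 2 working days. A reader might infer that a real GVHD increase would pass unreviewed; the documents do not support that. This part of the reply stands, and it limits the point to the pre-specified prompt.

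A reader might also infer that the plan demands six times stronger evidence of harm than of benefit, because 12.5 chooses to "use a one-sided type I error rate of 0.15 with 80% power" and 0.15/0.025 = 6. That comparison is not like for like. The 0.15 belongs to the single design test of PFS. The 0.05 applies at repeated looks to two safety rates, at which no efficacy result can change the trial. The case for a lenient level rests on the low cost of a consultation, not on that ratio.

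Third, the plan claims no power for the trigger, and small numbers are a main cause of its weakness. At two-sided 0.05, 80% power for 18% v 9% would need 226 per arm; even at one-sided 0.15 it would need 101. This also stands: a changed threshold helps but cannot make the trigger powerful.

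Finally, the documents give no basis for 0.10 in particular. That is correct; the exact level is the sponsor's choice.

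**Conclusion.** The concern holds as a weakness of design and specification, not as an error in any stated figure. As written, the trigger misses a doubling from 9% in roughly 70% to 80% of trials, and a doubling from 4% in roughly 84% to 95%. The range is due to the unnamed test. Half of its two-sided level serves a direction that needs no review.

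The result assumes uniform accrual, looks at 39 and 53 per arm, and every vaccinated patient evaluable for acute GVHD at the look. Incomplete follow-up at the first look would make detection somewhat worse. The arithmetic covers GVHD only: the plan gives no baseline for grade 3 or higher treatment-related toxicity, so for that rate the argument rests on direction and the missing test alone.

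**What to change.** In 12.7, define the trigger as a GVAX rate higher than placebo, one-sided, at a level more lenient than the present 0.025 in that direction. Name the test, for example one-sided Fisher exact at 0.10, for both monitored rates. Print the event counts that trigger at the planned looks. At 39 per arm these are 4 v 0, 6 v 1, 7 v 2 and 8 v 3 (GVAX v placebo); the same hypergeometric calculation at 53 per arm gives 4 v 0, 6 v 1, 7 v 2 and 9 v 3. Keep DSMB consultation as the only consequence, and state the chance of firing so that the board knows what silence means.

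The cost is a change of wording and a short table. Sample size and the efficacy type I error are unaffected. The chance of an unneeded consultation is about 6% per endpoint at 9% v 9%; if the second endpoint behaved alike and independently, 1 − 0.94² = about 12% over both. A one-sided 0.10 score test would detect more, but at about 15% per endpoint and firing at 2 v 0. The gain is largest if Fisher is the test now intended (21% to 46% at 18% v 9%) and smaller if it is chi-square (31% to 46%). A doubling from 4% would still be missed in about 80% of trials, and the plan should say so.
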